10. Informed about the study methods and having given their consent		

EXCLUSION CRITERIA

	YES	NO
11. Previous systemic treatment		

12. Patients who are pregnant or breastfeeding 13. Any contraindications to Sunitinib in accordance with the text in the SmPC **INITIAL TREATMENT OF PATIENT WITH METASTATIC RENAL CELL**

Date of initial diagnosis of renal carcinoma |_____|_____|_____|2|0|____| (dd/mm/yyyy)

Date of initial diagnosis of metastatic renal cell carcinoma (date of initial discovery of the first metastases) |_____|_____|_____|2|0|____| (dd/mm/yyyy)

Sunitinib treatment start date |_____|_____|_____|2|0|1|____| (dd/mm/yyyy)

NEPHRECTOMYNephrectomy YES NO If yes, date |_____|_____|_____|2|0|1|____| (dd/mm/yyyy)

• Type of nephrectomy:

 radical	 partial
 with adrenalectomy	 without adrenalectomy
 with lymphadenectomy	 without lymphadenectomy
 open	 laparoscopic

HISTOLOGY

• Pathoanatomic classification:

- Clear cell carcinoma
- Multilocular cystic clear cell carcinoma
- Papillary cell carcinoma
- Chromophobe cell carcinoma
- Bellini's collecting duct carcinoma
- Medullary cell carcinoma
- Sarcomatoid contingent
- Other(*please specify*):

YES	NO
	

• Tumor size |_____|_____| mm

• TNM classification: T |____| N |____| M |____|

• Fuhrman nuclear grade: I |____| II |____| III |____| IV |____|

YES	NO
	
	
	

• Presence of necrosis? • Vascular embolism • Sarcomatoïdis composante **BLOOD SAMPLING BEFORE START OF SUNITINIB***** A delay of 6 weeks is tolerated between initiation and sampling**

YES	NO
	

- Blood sample of 2 times 5 ml

Sampling date |_____|_____|_____|2|0|1|____| (dd/mm/yyyy)

Histological sample of primitive tumor		
Sampling date ____ ____ ____ ____ ____ ____ ____ (dd/mm/yyyy)		

DATA RELATING TO THE STATUS OF A PATIENT WITH mRCC BEFORE START OF SUNITINIB

METASTATIC SITES		

- Lymph nodes		
o Supradiaphragmatic		
o Infradiaphragmatic		
- Recurrence at the nephrectomy renal bed		
- Other		
(please specify):		

BLOOD SAMPLING AT 6 MONTHS		
	YES	NO
- Blood sample of 2 times 5 ml		
Sampling date __ __ __ __ __ __ __ (dd/mm/yyyy)		

DATA RELATING TO PATIENTS WITH mRCC AFTER 12 MONTHS OF TREATMENT WITH SUNITINIB

Visit date |__|_|__|_|__|_|2_|0_|1_|__| (dd/mm/yyyy)

Sunitinib Actual dose 50mg 37,5mg 25mg

Actual schema 4/2 2/1 Continu

CLINICAL ASSESSMENT ACCORDING TO RECIST v 1.1

Partial response Yes No

Percentage tumor reduction: %

Complete response Yes No

If yes, the patient should move to the arm of patients in CR

Stable disease Yes No

Progression Yes No

If yes: Date of progression |__|_|__|_|__|_|2_|0_|1_|__| (dd/mm/yyyy)

If yes: Progression at a known metastatic site Yes No

New metastatic site Yes No

METASTATIC SITES

LOCALIZATION OF METASTASES	YES	NO
- Lungs		
- Bone		
- Liver		
- Adrenal glands		
- Pancreas		
- Brain		
- Lymph nodes		
o Supradiaphragmatic		
o Infradiaphragmatic		
- Recurrence at the nephrectomy renal bed		
- Other		
(please specify):		

NUMBER OF METASTATIC SITES: |__|

BLOOD SAMPLING AT 12 MONTHS

	YES	NO
- Blood sample of 2 times 5 ml		
Sampling date __ _ __ _ __ _ 2_ 0_ 1_ __ (dd/mm/yyyy)		

DATA RELATING TO PATIENTS WITH mRCC DURING DISEASE PROGRESSION

Visit date |_____|_____|_____|_____|_2_|_0_|_1_|____| (dd/mm/yyyy)

CLINICAL ASSESSMENT ACCORDING TO RECIST v 1.1

Date of disease progression |_____|_____|_____|_____|_____|_2_|_0_|_1_|____|
(dd/mm/yyyy)

Progression at a known metastatic site

Yes No

New metastatic site

Yes No

METASTATIC SITES

LOCALIZATION OF METASTASES

YES **NO**

- Lungs
- Bone
- Liver
- Adrenal glands
- Pancreas
- Brain
- Lymph nodes
 - o Supradiaphragmatic
 - o Infradiaphragmatic
- Recurrence at the nephrectomy renal bed
- Other

(please specify):

NUMBER OF METASTATIC SITES: |____|

BLOOD SAMPLING DURING PROGRESSION

YES **NO**

- Blood sample of 2 times 5 ml

Sampling date |_____|_____|_____|_____|_____|_2_|_0_|_1_|____| (dd/mm/yyyy)

**Data relating to the end of study visit of patients NOT in CR
(36 months)**

Did the patient attend a visit at 36 months	YES 	NO 
Visit date __ __ __ __ _2_ _0_ _1_ __ (dd/mm/yyyy)		
Is the patient still being treated with Sunitinib? YES		NO 
If yes, is the patient presenting a:		
PARTIAL RESPONSE	YES 	NO 
COMPLETE RESPONSE	YES 	NO 
STABLE DISEASE	YES 	NO 
PROGRESSION	YES 	NO 
If no, is the patient presenting disease PROGRESSION	YES 	NO 
Please specify the new treatment:		
Sunitinib discontinuation date __ __ __ __ _2_ _0_ _1_ __		
Number of previous lines of treatment.....		
LATEST INFORMATION		
Did the patient withdraw from study prematurely? YES	 NO 	
Latest information date: __ __ __ __ _2_ _0_ _1_ __ (dd/mm/yyyy)		

DEATH		
YES 	NO 	
Date of death: __ __ __ __ _2_ _0_ _1_ __ (dd/mm/yyyy)		

13.7. Appendix 7: Laboratory tests

	Conventional units	Conversion factor	SI units
Hematology			
Erythrocytes	10 ⁶ /mm ³	x 10 ⁶	10 ¹² /l
Hemoglobin (Hb)	g/dl	x 10	g/l
Platelet count	10 ³ /mm ³	x 10 ⁹	10 ¹² /l
Leukocytes	10 ³ /mm ³	x 10 ⁶	10 ⁹ /l
Leukocyte differential count	%	x 0.01	fraction
Schistocytes			
Haptoglobin			
Biochemistry			
Total bilirubin	mg/dl	x 17.1	µmol/l
Alanine aminotransferase (ALT)	U/l	ND	U/l
Aspartate aminotransferase (AST)	U/l	ND	U/l
Alkaline phosphatase	U/l	ND	U/l
Lactate dehydrogenase (LDH)	U/l	ND	U/l
Amylase	U/l	ND	U/l
Lipase	U/l	ND	U/l
Total protein	g/dl	x 10	g/l
Albumin	g/dl	x 10	g/l
Sodium	mEq/l	x 1.0	mmol/l
Potassium	mEq/l	x 1.0	mmol/l
Calcium	mg/dl	x 0.25	mmol/l
Phosphorous	mg/dl	x 0.323	mmol/l
Creatinine	mg/dl	x 88.4	µmol/l
Uric acid	mg/dl	x 0.059	mmol/l
Glucose	mg/dl	x 0.055	mmol/l
TSH	mU/l	ND	mU/l
Thyroxine T4	ng/dl	x 12.9	pmol/l
Coagulation			
Prothrombin time PT	seconds	ND	seconds
Activated partial thromboplastin time aPTT	seconds	ND	seconds
International normalized ratio INR	%	ND	%
Urinalysis (test strip)			
Protein	ND		
Glucose	ND		
Blood	ND		
Ketones	ND		
Albuminuria			
Creatinuria			

13.8. Appendix 8: Prognostic factors

- ECOG performance status

- 0 Fully active, able to carry on all predisease activities without restriction.
- 1 Patient restricted in physically strenuous activity but ambulatory and able to carry out work of a light or sedentary nature, for example, light housework or office work.
- 2 Patient ambulatory and capable of all self-care but unable to carry out any work activities. Up and about more than 50% of the waking hours.
- 3 Capable of only limited self-care, confined to bed or chair 50% or more of waking hours.
- 4 Patient completely disabled. Cannot carry on any self-care. Totally confined to bed or chair.
- 5 Patient is dead.

- Number of metastatic sites

- Length of time interval between diagnosis and start of systemic treatment

- Hemoglobinemia

- LDH

- Corrected calcium

- Alkaline phosphatases

13.9. Appendix 9: RECIST v 1.1 assessment criteria

This section presents the definition of the criteria used to determine the objective tumor response of target lesions.

- Assessment of target lesions

Complete response (CR): Disappearance of all target lesions. Pathological lymph nodes (target or non-target) must show a reduction of the short axis to a size of < 10 mm.

Partial response (PR): Reduction of at least 30% of the sum of the diameters of the target lesions, taking the sum of the initial diameters as a reference.

Disease progression (DP): Increase of at least 20% of the sum of the diameters of the target lesions, taking the lowest sum in the study as the reference (including the initial sum if this is the lowest sum in the study). In addition the relative increase of 20%, the sum must also show an absolute increase of at least 5 mm. (Note: the appearance of one or more new lesions is also considered progression).

Stable disease (SD): Absence of sufficient reduction for a PR or absence of a sufficient increase for DP, taking as reference the sum of the lowest diameters during the study.

- Assessment of non-target lesions

This section presents the definition of the criteria used to determine the tumor response of non-target lesions. Although some non-target lesions may actually be measurable, it is not necessary to measure them; they must only be assessed qualitatively at the times specified in the protocol.

Complete response (CR): Disappearance of all non-target lesions and normalization of tumor marker levels. All lymph nodes must have non-pathological dimensions (minor axis < 10 mm).

No CR/No DP: Persistence of one or more non-target lesions and/or maintenance of the level of tumor marker above normal limits.

Disease progression (DP): The appearance of one or more new lesions is also regarded as progression.

13.10. Appendix 10: Centralized reading CT SCANS

In this study, patients in CR (CAS) shall be granted prior to final inclusion in the study of a central review of two of their scanner :

- The baseline scan (performed at initiation of Sutent in the first line)
- The scanner showing complete response

This league will replay between the screening visit and the visit to include a patient .

For that scanners will be engraved on 2CD -ROM:

- 1 for the baseline scan (performed at initiation of Sutent in the first line)
- 1 for the scanner showing complete response

Scanners should be sent immediately after the screening visit at IGR accompanied by the screening sheet printed from the e -CRF . 2 CD- ROM by patient and envelopes will be provided by Pfizer .

Contact and address for sending CD- ROM

Contact:

PPD [REDACTED]

PPD [REDACTED]

PPD [REDACTED]

[REDACTED] France

Telephone: PPD [REDACTED]

[figure not shown]
13.11. Appendix 11: Methods for collecting and transporting biological samples

For patients in complete remission (Cases)

- A whole blood sample will be collected during screening visit into two 5 ml EDTA tubes. These samples will be centrifuged and frozen to produce 2 aliquots (minimum) of plasma and 2 pellets of whole blood stored at -80 °C (see diagram below).
- A whole blood sample will be collected during disease progression (if it occurs) into two 5 ml EDTA tubes and processed in the same manner.

For patients screened as controls (2 sites)

- A whole blood sample will be collected before the start of Sunitinib into two 5 ml EDTA tubes and processed in the same manner.
- A whole blood sample will be collected **at 6 months** into two 5 ml EDTA tubes and processed in the same manner.
- A whole blood sample will be collected at 12 months into two 5 ml EDTA tubes and processed in the same manner.
- A whole blood sample will be collected **during disease progression** into two 5 ml EDTA tubes and processed in the same manner.

Storage and transport: These tubes will be stored at -80 °C and transported frozen to the laboratory by OCT Santé, accompanied by the form below.

IGR EXTERNAL SAMPLES HANDOVER FORM

APERÇU

CSET XXXX-XXXX

Investigator: [name]

Consultant CRA: ☎

Sponsor: IGR

Patient identification
(Stick patient label here)

Patient's inclusion/randomization no.:

Enrolling site:

VISIT: Cases

 screening visit PROGRESSION

Or Controls

 Before treatment 6 months 12 months Progression

Sampling date |_____| |_____| |_____| |2|0|1| | _____ Department:

➤ 2 x 5 ml EDTA tubes with "VIOLET" stopper _____ Sampling time: __ :__

[figure not shown]
⇒ Instructions: (gently invert the tubes of blood 6 to 8 times)

Nurse's name and signature:

Comments:

Laboratory services

Comments:

Laboratory services**2 x 5.0 ml EDTA**

**Centrifuge at 2000 g
for 10 min at +4 °C**

**LABELS ON
CRYOTUBES**

**2 aliquots
plasma 1.8 ml
NUNC EDTA
CRYOTUBES**

**2 whole blood pellets
1.8 ml NUNC EDTA
CRYOTUBES**

Aliquot 1 **pellet** in box number: ----- Position:

Aliquot 2 **pellet** in box number: ----- Position:

13.12. Appendix 12: Methods for collecting and transporting histological samples

For patients in complete remission (**Cases**) and screened as controls (**Control**)

A histological specimen, if available, will be sent during the screening or inclusion visit. These samples will be labeled (as indicated below) and sent by post to the IGR.

CSET XXXX-XXXX **Prom: IGR**
Proto: APERcU
Investig: Dr [REDACTED] **PPD**
Arc: [REDACTED]

Storage and shipment: These slides will be stored at room temperature and transported by post to the laboratory accompanied by the sheet below.

13.13 Appendix 13: Sutent – product characteristics summary

Summaries of product characteristics are available at the following links

<http://base-donnees-publique.medicaments.gouv.fr/extrait.php?specid=69225978>

<http://base-donnees-publique.medicaments.gouv.fr/extrait.php?specid=65283820>

<http://base-donnees-publique.medicaments.gouv.fr/extrait.php?specid=63841059>

A printable version will be provided to participating physicians during the implementation of the study.

13.14 Appendix 14: Blood markers of angiogenesis: rationale, parameters analyzed and guidelines Rationale

On the one hand, angiogenesis involves a myriad of angiogenic growth factors and inhibitors synthesized by tumor and stromal cells and, on the other hand, endothelial cells (ECs) and their progenitors. The proliferation of ECs is activated by powerful stimulators, released by tumor cells, vascular endothelial growth factor (VEGF) and basic fibroblast growth factor (bFGF).

It is important to remember that angiogenesis and hemostasis are linked to blood clotting and to fibrinolysis, which directly influence tumor angiogenesis. In fact, activated platelets release numerous angiogenic growth factors such as VEGF, bFGF, SDF-1 and platelet-derived growth factors (PDGFs) and they contribute to tumor angiogenesis within a potentially prothrombotic tumoral microcirculation [1,2].

Angiogenesis markers will be assessed in order to study the role they might play in the prediction of renewed disease progression.

Angiogenesis blood markers analyzed

The plasma levels of the following angiogenic factors will be quantified by ELISA:

- VEGF - prognostic factor of the angiogenesis pathway; target of the antiangiogenic treatment administered.
- bFGF - the levels of which correlate with the prognosis of certain solid tumors and whose proliferative action on endothelial cells is inhibited *in vitro* by
- SDF-1 - synthesized in response to hypoxia. It has a chemoattractive effect on endothelial cells and thus contributes to tumor angiogenesis [3].
- The soluble receptors of VEGF (sVEGFR1 and s VEGFR2), which reduce the angiogenic activity of VEGF.
- The 3 isoforms of PDGF (-AA, -BB and -AB) act on pericytes.

Objectives

- To assess the prognostic value of plasma VEGF in a complete response and progression context
- To study other angiogenesis markers as indicators of a complete tumor response to Sunitinib.

Schedule

The peripheral whole blood collected into EDTA tubes will be tested:

FOR CASES:

2 x 5 ml EDTA tubes will be collected during the screening visit or during the inclusion visit and in the event of disease progression.

FOR CONTROLS:

2 x 5 ml EDTA tubes will be collected before starting Sunitinib, at 6 months, at 12 months and during disease progression with Sunitinib.

Histological specimens (if available) will be tested:

For cases and for controls:

A histological block or 15 slides of histological sampling of the primary tumor performed before the screening visit.

Guidelines for the sampling, processing, storage and transport of blood samples. The assessment of blood markers of angiogenesis will be centralized at the IGR.

EDTA tubes: assessment of plasma markers of angiogenesis. After 2 rounds of centrifugation at 2000 g at 20 °C for 10 minutes, the plasma will be stored at a temperature of < -20 °C or, preferably, at -80 °C.

Delivery address: Biological Resources Center
Biopathology Department
Institut Gustave Roussy
[name]
[name]
[contact]

References

- 1- Niedrodzik ML & Karpatkin S. Thrombin induces tumor growth, metastasis and angiogenesis: Evidence for a thrombin-regulated dormant tumor phenotype. *Cancer Cell*, 2006;10:355-362.

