8.1.1. Type of study

It is a cross-sectional then longitudinal, comparative, multicenter, prospective, case-control observational study with collection of blood samples.

In addition to the patient's usual medical treatment, as described in the HAS's long-term diseases guide, validated by a multidisciplinary working group ¹⁹, the specific monitoring methods provided for in this research comprise of:

- Blood sampling of 2 times 5 ml into 2 EDTA tubes done at screening visit during CR and during disease progression, if it occurs, in the 40 patients with metastatic renal cell carcinoma in CR with Sunitinib (**Cases**).
- Blood sampling of 2 times 5 ml into 2 EDTA tubes done before starting Sunitinib, at 6 months, at 12 months and during disease progression, in 80 patients with metastatic renal cell carcinoma without CR with Sunitinib throughout the 36 months of the study (**Controls**).

Therefore, these monitoring methods only involve negligible risks and constraints.

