The CD-ROM will be send just after the screening visit to the IGR with the screening visit printed with e-CRF, 2 CD-ROM by patient and the envelopes will be provided by Pfizer.

Contact and address for the sending of the CD-ROM :

[name]

PPD

Telephone : PPD

F) Establishment of a bank of blood samples (see Appendix 11)

For patients with metastatic renal cell carcinoma in CR with Sunitinib (Cases)

- One blood sample of 2 times 5 ml will be collected during screening visit
- One blood sample of 2 times 5 ml will be collected in the event of disease progression

If the sample are not available during the screening visit, a six week time limit is authorized between screening and sample.

For patients with metastatic renal cell carcinoma without CR at the start of Sunitinib and during the 36 months of the study (Controls)

- One blood sample of 2 times 5 ml will be collected before starting Sunitinib, at 6 months, at 12 months and during disease progression.

All samples will be centrifuged and frozen to produce 2 aliquots (minimum) of plasma and 2 pellets of whole blood. These tubes will be labeled, stored at -80 °C and transported frozen for centralized storage at the IGR's biobank, which is the responsibility of [name] and [name]

The biomarkers studied in these blood samples will be as follows: FGF, IL-8, PIF and analysis of single nucleotide polymorphisms (SNPs) of VEGF. This list is not exhaustive. Other biomarkers may be examined, following agreement from the Scientific Committee, depending on how basic knowledge advances.

G) Establishment of a bank of histological samples (see Appendix 12)

In view of the progress made in the context of histological analyzes, these one would make it possible to detect certain markers predictive of a complete response.

Participating physicians and pathologists are encouraged to submit histologic sample, if available, as a block or failing 4µm white slides. The histological sample will be from the primary tumor.

These will be used for genomic and immune histochemical analyzes. These analyzes will aim to identify predictive biomarkers of complete response.

If the samples were not taken or were not planned, they should not have been made in the specific context of this observational study.

Tissue fixation should be performed in 10% buffered formalin at neutral pH (pH 7.2-7.6 aqueous)

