8.2. Setting

8.2.1. Population of physicians/health care professionals

The active participation of 15 - 20 oncologists ensures conditions of sufficient statistical accuracy to meet the objectives of the study.

Each physician will include patients with metastatic renal cell carcinoma in CR with Sunitinib (**Cases**).

The teams of [name] (IGR), of [name] (PPD) including doctors PPD and PPD , of [name] (PPD), of [name] (PPD), of [name] (PPD) will include 80 patients with metastatic renal cell carcinoma without CR at the start of Sunitinib administration. This is the control population. Given the rarity of the CR event observed (1.7%), it is expected that none of the patients in the control group (n = 80) will present CR with Sunitinib. **If any of the 80 controls present CR with Sunitinib during follow-up, s/he will be moved to the Cases group.**

These patients are seen in consultation and meet the inclusion and exclusion criteria.

The study's scientific committee has identified 25 sites that are likely to participate in this project. These sites have all been contacted (by email and by telephone) as part of a feasibility study (Appendix 14). At the end of this process, twenty sites have agreed to participate in the study.

If the evaluation of the number of patients that can be included by those 20 sites remains below 40 **Cases** and 80 **Controls**, the pool of participating physicians may be increased.

A description of the population of physicians will be made retrospectively on the basis of the identification data for the participating physicians (gender, age, location etc.).

In order to ensure the external validity of the study, it will then be verified that the population of participating physicians is representative of the total population of oncologists in France.

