13.15 Appendix 15: Analysis of genetic polymorphisms

Rationale

The isoforms of VEGF-A are encoded by a single gene at locus 6p12. Although no polymorphisms have been identified in the coding regions, several allelic polymorphisms located in the promoter region 5' of exon 1 or in the UTR region of exon 8 may explain the variations between individuals in the production of VEGF (1). It has been reported that significant variations in the blood levels of VEGF during hypoxia or during coagulation disorders correlate with polymorphisms (2, 3). Given the important pathophysiological role of angiogenesis in the development of clear cell carcinomas, it will be interesting to see whether these polymorphisms correlate with the occurrence of a complete response.

Sunitinib is an active treatment of renal cell carcinoma that acts by inhibition of the tyrosine kinases of VEGFR-1 and 2. Because elevated blood levels of VEGF, as well as significant quantities of VEGF bound to the extracellular matrix, can influence the efficacy of Sunitinib, it will also be interesting to examine the link between constitutional polymorphisms of VEGF and the occurrence of a complete response with Sunitinib.

Due to interference with one of the strongest targets of Sunitinib, VEGFR-2, polymorphisms may also perturb the level of response.

Polymorphisms analyzed

The non-exhaustive list of the polymorphisms that will be analyzed includes the analysis of the polymorphisms of the different VEGFRs and VEGF. The analysis of polymorphisms will be done by DNA sequencing after PCR amplification. The assessment of polymorphisms will be done at the end of the study.

Guidelines for the sampling, processing, storage and transport of blood samples.

2 EDTA tubes containing 5 ml samples (see Appendices 10 and 12) will produce 2 pellets of whole blood and allow the extraction of DNA for analysis of polymorphisms.

Delivery address:

Biological Resources Center
Institut Gustave Roussy
[name]
[name]

References

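### Blood handling, six-week and tissue-timing rules conflict across sections, and cases have no scheduled pre-Sunitinib plasma: reconcile them and keep case-control plasma findings descriptive

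*Protocol*

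**What the plan says.** **Blood schedule.** Cases must already have reached CR, within the preceding five years (Protocol 3.2.2, 8.2.3). Section 8.1.1 has their blood "done at screening visit during CR and during disease progression, if it occurs"; Appendix 14 has it "collected during the screening visit or during the inclusion visit and in the event of disease progression". Control blood is "done before starting Sunitinib, at 6 months, at 12 months and during disease progression" (8.1.1). A control who reaches CR moves to the case group, but "it is expected that none of the patients in the control group (n = 80) will present CR with Sunitinib" (8.2.1).

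**Purpose.** Section 9.4.3 assigns the case inclusion sample to markers of CR, the control inclusion, 6- and 12-month samples to prediction of response, and the progression samples to prediction of recurrence. Section 6 asks whether serum or histologic markers might predict recurrence or CR. Sections 3.1 and 7 compare cases with controls without naming a control time point. SAP 2.4 leaves biomarkers to a separate plan.

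**Processing.** Appendix 11 spins the tubes at 2000 g "for 10 min at +4 °C" and stores at -80 °C. Appendix 14 stores the plasma "After 2 rounds of centrifugation at 2000 g at 20 °C for 10 minutes", below -20 °C or preferably at -80 °C. Section 8.1.4 F, "Establishment of a bank of blood samples (see Appendix 11"), cites only the first. Appendix 15 has "2 EDTA tubes containing 5 ml samples (see Appendices 10 and 12"), which are the CT-reading and histology appendices.

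**Six-week allowance and tissue timing.** Each is stated in several places with different anchors, set out under the working.

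**The concern.** A plasma level measured in remission, possibly on drug and up to five years after CR, is not comparable with a control level measured before treatment with tumour present. The 6- and 12-month control draws do not match it either, because those patients are not in CR. A difference would mix the CR state with tumour burden, drug exposure and time since CR, so it cannot by itself show what predicts CR. If the separate biomarker plan does not fix the contrast, such a difference could be reported as predictive.

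The handling and timing conflicts add to this. Sites centrifuge before shipping (8.2.5.2), so a site following one appendix may process differently from a site following the other. A control sample filed as baseline may have been drawn after Sunitinib started. Tissue described as pre-treatment in one section may not be so under another.

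**Working it through.** **1. The plan's own figure.** Inputs: 40 cases, 80 controls, two-sided 5%, d = 0.55 (Protocol 8.5.1, SAP 2.5, 4.1). Noncentrality = 0.55 × √(40 × 80 / 120) = 2.84 on 118 degrees of freedom, giving power 0.804; the d detectable at 80% power is 0.547. The stated 80% is reproduced and not disputed. It assumes 40 and 80 usable values at a meaningful common time point.

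**2. Pre-Sunitinib plasma from patients who reach CR.** Cases recruited in CR: 0 of 40 by schedule. Converting controls: X ~ Binomial(80, p), with p = 1.7% from 8.2.1 and 1% to 3% from section 6.

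| p | Expected, 80p | P(none), (1-p)^80 | 95th percentile |
|---|---|---|---|
| 1% | 0.80 | 0.448 | 2 |
| 1.7% | 1.36 | 0.254 | 3 |
| 3% | 2.40 | 0.087 | 5 |

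As an illustration only, assume 2 converters against 78 other controls: power for d = 0.55 is 12%, and the detectable d is 2.03. The planned power does not carry over to a pre-treatment plasma contrast.

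**3. Processing of the same 2 x 5 ml EDTA tubes.**

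| | Appendix 11 | Appendix 14 |
|---|---|---|
| Force and time | 2000 g, 10 min | 2000 g, 10 min |
| Temperature | +4 °C | 20 °C |
| Spins | one shown | two rounds |
| Storage | -80 °C | below -20 °C, preferably -80 °C |

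The temperature and storage differences are explicit. The spin count is uncertain, because part of Appendix 11 is not in the text available. Appendix 14 does not defer to Appendix 11, and the Appendix 15 cross-reference cannot settle the matter.

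**4. Six-week rules, by group.**
- Cases: 8.1.4 B and F count from screening to sampling. The case inclusion page in Appendix 5 counts from initiation to sampling, under a heading that places sampling before Sunitinib. A patient enrolled in CR cannot meet that heading. The Appendix 5 screening page and the Appendix 11 handover form have the right visit.
- Controls: 8.1.4 C counts from screening to inclusion, although 8.1.4 B reserves the screening form for cases. Appendix 6 counts from initiation to sampling, under a heading of sampling before Sunitinib. It does not say on which side of initiation the six weeks fall.

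**5. Tissue timing.**
- Before Sunitinib: 3.1 and aim d of section 6.
- At diagnosis: 8.1.3.
- When initiating Sunitinib: SAP 2.2.2.
- During CR and at recurrence: section 7.
- Before the screening visit: Appendix 14. For a case this can be after Sunitinib started.
- At case progression as well: 8.2.5.2.

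**The case against.** The strongest reply is that the protocol already draws the line in the right place. Section 9.4.3 makes case blood descriptive and keeps prediction of response within controls. Aim c of section 6 ties the blood bank to CR and recurrence, Appendix 14 speaks of indicators of CR, and 8.1.4 G gives prediction of CR to histology. The section 6 question can be read as serum for recurrence and histology for CR. The biomarker plan, which we do not have, may name the control time point. Most of this stands. A reader might infer that the study sets out to claim plasma predictors of CR from post-CR samples; the documents do not support that. What remains is one loosely worded question and two objectives silent on timing.

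On processing, 8.1.4 F points to Appendix 11 alone, and that appendix carries the form that travels with the tubes, so sites may all have followed it. A reader might infer that the conflict biases the case-control contrast. That would require use of the two procedures to differ by group. A route exists, since all physicians recruit cases while controls come from named teams (8.2.1), but nothing shows that it happened.

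The Appendix 6 note may mean six weeks before initiation, which would be harmless; the text leaves it open. The six-week rules are also not one three-way contradiction, since some govern cases and others controls. The section 7 tissue line lists markers that overlap the blood panel, so it may be a slip.

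**Conclusion.** The point holds as a set of conflicts to reconcile plus a limit on interpretation, and it should be fixed. The explicit conflicts are centrifugation temperature, storage limit, the Appendix 15 cross-reference, the case form heading, the six-week anchors within each group, and tissue timing.

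For plasma, pre-treatment samples from patients reaching CR are expected to number about 1.4 at 1.7% (0.8 to 2.4 at 1% to 3%), against 40 planned cases. This assumes that all 80 controls are enrolled and sampled at baseline, and convert independently at the quoted rates. No analysis plan can create the missing case samples; it can only choose the contrast and state what it means.

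The size of any processing effect is unknown, because the documents give no shift between procedures. Mixed use would add measurement noise.

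The consequence should not be stretched further. The primary objective does not depend on these samples. Within-case comparison of CR with recurrence, and within-control study of baseline plasma against response, both remain open. Germline SNPs do not change with sampling time, but a case-control SNP difference is not thereby clean evidence of prediction. Cases may be enrolled up to five years after CR, so they are survivors, and they do not face the life-expectancy, laboratory and no-prior-systemic-treatment criteria set for controls.

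**What to change.** (a) With the biobank, reconcile Appendices 11 and 14 to one centrifugation and storage procedure, and correct the Appendix 15 cross-reference. Record the procedure used for each sample, allowing unknown as an answer, for a sensitivity analysis.

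(b) Correct the sampling heading on the case inclusion page of Appendix 5. Reconcile the six-week rule separately for cases (8.1.4 B, 8.1.4 F, Appendix 5) and controls (8.1.4 C, Appendix 6). Use the Sunitinib start and sampling dates already on the control form to flag samples taken after start, and exclude them from baseline analyses.

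(c) Carry the 9.4.3 distinction into 3.1, 7 and Appendix 14: case-control plasma differences describe the CR state, prediction of response is studied within controls, and the biomarker plan names the control time point.

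(d) Reconcile the tissue statements (3.1, 6, 7, 8.1.3, 8.2.5.2, Appendix 14, SAP 2.2.2). Limit tissue claims about predictors of CR to samples dated before Sunitinib start. Report SNP comparisons with the caveat on survivorship and differing eligibility.

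The cost is wording, form notes and a memo to sites, with no new visits or patients. The downsides are a narrower plasma claim, some samples excluded or of unknown processing, and tracing of banked samples: at most 40 × 2 + 80 × 4 = 400 scheduled draws, or 40 + 80 × 3 = 280 without the progression draws.
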